8. SOFTWARE

All analyses will be done using SAS Version 9.4 or higher.

10. APPENDIX

10.1. Summary of Statistical Analyses

Primary Efficacy Analysis:

Endpoint	Analysis Populations	Estimand	Statistical Method	Supportive Analysis	Subgroup Analysis	Other Analyses
Primary Endpoint						
Percent change from baseline in calculated LDL-C at week 24	ITT	ITT estimand: The calculated LDL-C at week 24 will be the LDL-C value obtained within the week 24 efficacy analysis window, regardless of adherence to treatment and subsequent therapies.	MMRM	Yes	Yes	
 1. mITT 2. PMM (randomized population) 3. MMRM using strata based on observed data

10.2. Windows for Analysis Time Points

Below are the definitions for the visit windows programmatically imposed on measures repeatedly collected over the course of the study. These visit windows reflect the study schedule of assessments as described in the protocol.

The visit windows are constructed using ranges applied to the number of days in study (study days) when the measure is collected. Below are the relevant definitions for the analysis visit windows:

1. Study day is defined as the number of days since the first study treatment administration +1. The first study treatment occurs on
2. Study Day 1.
3. Open-label study day is defined as the number of days since the first open-label study treatment administration+1
4. Since the protocol specifies that measurements be collected before study treatment is administered on a given day, it is appropriate that baseline include Day 1.
5. For randomized but not treated patients, Day 1 is the day of randomization.

Table 1: Global Analysis Windows

Visit label	Targeted Study Day	Targeted Open-Label Study Day	Analysis Window in Study Day
Screening	< Day 1	N/A	Measurement obtained prior to first study treatment, and not defined as baseline visit
Baseline	1	N/A	Measurement obtained closest to first study treatment, while remaining prior to first study treatment
Week 2	15	N/A	2 to 21
Week 4	29	N/A	22 to 42
Week 8	57	N/A	43 to 70
Week 12	85	N/A	71 to 98
Week 16	113	N/A	99 to 126
Week 20	141	N/A	127 to 154
Week 24	169	Day 1	155 to 182 for patients not entering OLTP or 155 to first OL treatment day for patients entering OLTP
Week 28	197	29	first OL treatment day+1 to 210
Week 32	225	57	211 to 238
Week 36	253	85	239 to 266
Week 40	281	113	267 to 294
Week 44	309	141	295 to 322
Week 48	337	169	323 to 350
FU – W4	For patients prematurely discontinued trt: last study trt to 28 days after last study trt For patients completed OLTP: 365	For patients prematurely discontinued trt: last study trt to 28 days after last study trt For patients completed OLTP: 197	For patients prematurely discontinued trt: Last study trt day +1 to 56 days after last study trt For patients completed OLTP: 351 to 392
FU – W12	For patients prematurely discontinued trt: last study trt to 84 days after last study trt For patients completed OLTP: 421	For patients prematurely discontinued trt: last study trt to 84 days after last study trt For patients completed OLTP: 253	For patients prematurely discontinued trt: 57 days after last study trt to 112 days after last study trt

Visit label	Targeted Study Day	Targeted Open-Label Study Day	Analysis Window in Study Day
FU – W20	For patients prematurely discontinued trt: last study trt to 140 days after last study trt For patients completed OLTP: 477	For patients prematurely discontinued trt: last study trt to 140 days after last study trt For patients completed OLTP: 309	For patients prematurely discontinued trt: 113 days after last study trt to 168 days after last study trt For patients completed OLTP:449 to 504
FU > W20	N/A	N/A	For patients prematurely discontinued trt: >168 days after last study trt For patients completed OLTP:>504

Study days are calculated from the day of first double-blind IMP administration, the day of first double-blind IMP administration being Day 1. For randomized but not treated patients, Day 1 is the day of randomization.

Table 2: Efficacy Analysis Windows – Statistical Testing

Visit Label	Targeted study day	Analysis window in study days
Screening	< Day 1	Measurement obtained prior to first study treatment, and not defined as baseline visit
Baseline	1	Measurement obtained closest to first study treatment, while remaining prior to first study treatment
Week 2	15	2 to 21
Week 4	29	22 to 42
Week 8	57	43 to 70
Week 12	85	71 to 98
Week 16	113	99 to 126
Week 20	141	127 to 154
Week 24	169	155 to 182 for patients not entering OLTP or 155 to first OL treatment day for patients entering OLTP

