6.3. Premature Withdrawal from the Study

A patient has the right to withdraw from the study at any time, for any reason, and without repercussion.

The investigator and/or sponsor have the right to withdraw a patient from the study if it is no longer in the interest of the patient to continue in the study, or if the patient's continuation in the study places the scientific outcome of the study at risk (eg, if a patient does not or cannot follow study procedures). An excessive rate of withdrawals would render the study uninterpretable; therefore, unnecessary withdrawal of patients should be avoided.

Patients who are withdrawn prematurely from the study will be asked to complete study assessments, as described in Section 8.1.5.

Rules for discontinuation of study treatment (permanent or temporary) are discussed in Section 7.4.2.

Early Termination from the Study

If for any reason the patient withdraws from the study prematurely, the patient should undergo an unscheduled visit with assessments normally planned at the end of the double-blind treatment visit if the patient is in the DBTP, or the end of the open-label treatment visit, if the patient is in the OLTP. The visit should take place within 5 days of treatment discontinuation. The assessments completed should include pregnancy testing for WOCBP. The patient should be followed for at least 24 weeks from the last dose of study drug or up to recovery or stabilization of any AE to be followed-up as specified in this protocol, whichever comes last. A final end of study visit should take place with assessments as specified in the end of study visit (ie, follow up visit) at 24 weeks after the premature discontinuation of study drug.

Sexually active WOCBP who discontinue the study prematurely should be reminded at the unscheduled visit following treatment discontinuation to maintain highly effective contraceptive measures for 24 weeks after the last dose of study drug. At this visit, the patient will be provided 5 urine pregnancy tests with instructions to test for pregnancy 4 weeks after this visit and Q4W thereafter. The patient will also be notified of Q4W follow-up phone calls to confirm continued contraception use and pregnancy reporting and to obtain the results of the urine pregnancy test.

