5.10. Analysis of Pharmacokinetic Variables

Descriptive statistics of concentrations of total evinacumab, total ANGPTL3, total alirocumab and total PCSK9 will be presented. Mean concentrations of each analyte will be tabulated by visit and treatment group, with concentrations below the LLOQ set to zero.

Plots of the mean concentrations (linear and log scales) will be presented by nominal sampling time. Plots of the individual concentrations (linear and log scales) will be presented by actual sampling time. In the linear-scaled plots, concentrations below the LLOQ will be set to zero; in the log-scaled plots, concentrations below the LLOQ will be imputed as LLOQ/2.

Descriptive statistics will be provided for concentrations of statins at each sampling time. The ratio of concentration at week 24 over baseline will be presented for individual patient, when available.

Descriptive comparison of concentrations of evinacumab and total ANGPTL3 between Caucasian patients and Japanese patients may be performed, if sufficient data are collected.

When appropriate, relationship between concentrations of evinacumab and LDL-C or other biomarkers may be evaluated descriptively.

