6.4. Visit Windows

Visit windows will be programmatically imposed on those efficacy and safety measures repeatedly collected over the course of the study. These visit windows are derived from the number of days in study, specifically assigning day ranges to represent the study assessment schedule provided in the protocol. Data analyzed by time point (including efficacy, laboratory safety data, vital signs, ECG, quality of life, drug concentration and ADA) will be summarized using the analysis windows given in Appendix 10.2 (i.e. efficacy analysis windows for efficacy and global analysis windows for safety). These analysis windows will be applicable for all analyses, and they are defined to provide more homogeneous data for time point-specific analyses. If multiple valid values of a variable exist within an analysis window, the nearest from the targeted study day will be selected for analysis, unless otherwise specified. If the difference is a tie, the value after the targeted study day will be used. If multiple valid values of a variable

exist within a same day, then the first value of the day will be selected when time is available, else the scheduled visit will be selected.

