apheresis: Study assessments will be performed and blood samples will be collected immediately before the lipid-apheresis procedure; open-label study drug will be administered after the apheresis procedure.

15. In the OLTP, the HADS should be administered after the patients have been informed of their lipid results.

Schedule of Events – Follow-up Period

Study Procedure	Follow-up Period ⁵				
	16 ⁵	PV17 ^{5,6}	18 ⁵	PV19 ^{5,6}	EOS 20
Visit					
Day	365	393	421	449	477
Visit Window (Day)	±5	±5	±5	±5	±5
Week	52	56	60	64	68
Treatment:					
Concomitant Medications (including LMT and apheresis)	X	X	X	X	X
Query LMT Compliance	X	X	X	X	X
Safety:					
Adverse Events	X	X	X	X	X
Physical Examination					X
Measured Height					
Body Weight					X
Vital Signs (pulse rate, BP)					X
Electrocardiogram ¹					X
Tanner stage ²					X
Confirm contraception use and reminder of pregnancy reporting	X	X	X	X	X
Laboratory Testing:					
Lipid Panel	X		X		X
Specialty Lipid Panel	X		X		X
Hematology	X		X		X
Blood Chemistry	X		X		X
Creatine Phosphokinase	X		X		X
Serum Pregnancy Test ³					X
Urine Pregnancy Test ³	X	X	X	X	
Sex Hormones ²					X
Urinalysis					X
hs-CRP					X
HbA1C			X		X
PK and PD Samples					
ADA Sample					X
PK (evinacumab, alirocumab), ANGPTL3 Samples ⁴					X
Other:					
Review of diet					X

Footnotes for Schedule of Events –Follow-up Period

1. ECG should be performed before blood samples are collected at visits requiring blood draws.
2. Assessment of Tanner Stage and sex hormones (includes luteinizing hormone, follicle stimulating hormone, estradiol, total testosterone) only applicable to patients <18 years old.
3. WOCBP only, confirm required contraception use and reminder pregnancy reporting.
4. Including assay of total ANGPTL3.
5. For patients who discontinue prematurely or who opt out of the OL study.
6. Phone visits (PV) at weeks 56 and 64 to confirm required contraception use and obtain results of the home urine pregnancy test. Adverse events and concomitant medications will be collected.

Signature Page for VV-RIM-00083002 v1.0

ESig Approval	 15-Jul-2019 19:05:13 GMT+0000
ESig Approval	 15-Jul-2019 19:10:18 GMT+0000
ESig Approval	 15-Jul-2019 20:13:15 GMT+0000
ESig Approval	 16-Jul-2019 14:30:20 GMT+0000
ESig Approval	 16-Jul-2019 17:03:13 GMT+0000

Signature Page for VV-RIM-00083002 v1.0 Approved

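### SAP Table 1 sets premature discontinuers' follow-up windows 28 days earlier after last dose than completers', so their end-of-study PK and ADA samples can fall outside FU-W20 (minor)

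*SAP*

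**What the plan says.** SAP 10.2 introduces its windows with the statement "These visit windows reflect the study schedule of assessments as described in the protocol". The follow-up rows of Table 1 then give separate rules for two groups.

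- **Premature discontinuers:** targets are 28, 84 and 140 days after last study treatment.
- **Patients who completed the OLTP:** targets are study days 365, 421 and 477.
- **FU-W4 window:** "Last study trt day +1 to 56 days after last study trt For patients completed OLTP: 351 to 392".
- **FU-W20 window:** "113 days after last study trt to 168 days after last study trt For patients completed OLTP:449 to 504".
- **FU > W20:** later than 168 days after last treatment for discontinuers, later than day 504 for completers.

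The follow-up schedule in SAP 10.9 (Table 4 in the protocol) has visits on days 365, 393, 421, 449 and 477, each ±5 days. Its footnotes say who follows it, "For patients who discontinue prematurely or who opt out of the OL study", and that two of the contacts are calls: "Phone visits (PV) at weeks 56 and 64 to confirm required contraception use". Evinacumab concentration and ADA are sampled only at the last of the five, the end-of-study visit.

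For early terminators, Protocol 6.3 places the final visit "at 24 weeks after the premature discontinuation of study drug". Protocol 7.4.2 (open-label discontinuers) and 8.1.5 (all discontinuers) require at least 24 weeks from last dose.

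On use of the windows, SAP 6.4 lists data types including "quality of life, drug concentration and ADA) will be summarized using the analysis windows given in Appendix 10.2", and SAP 5.10 adds "Mean concentrations of each analyte will be tabulated by visit and treatment group".

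On disposition, SAP 4.5 counts patients completing the last follow-up visit, which it calls follow-up week 20. Protocol 10.4.1 instead counts follow-up as incomplete when the last visit is under 23 weeks after the last infusion. SAP 7 reports patients with insufficient follow-up without defining the term. SAP 1.2.4 lists no change on this point.

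**The concern.** One row label carries two clocks. For completers the follow-up weeks run from the end of the OLTP, and for discontinuers from the last dose, four weeks earlier. The protocol fixes the end-of-study visit relative to last dose for discontinuers, and the completers' visit falls at the same interval. Two patients sampled after the same washout can therefore appear in different rows of the concentration and ADA tables.

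The end-of-study sample is the only scheduled follow-up measurement of drug level and ADA. A by-visit mean that mixes or splits washout times is then harder to read. If the disposition count is built from the same rows, it can also depart from the protocol's own definition of completed follow-up.

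**Working it through.** **Inputs.** Last open-label dose on day 309 (Protocol 7.1). Week 48 visit on day 337, follow-up targets and windows (SAP Table 1). End of study at 24 weeks or later for discontinuers (Protocol 6.3, 7.4.2, 8.1.5). The 23-week rule (Protocol 10.4.1). Planned dropout 15% of 57 (SAP 2.2).

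**1. Reproduce the plan's completer targets.** 337 + 28 = 365; 337 + 84 = 421; 337 + 140 = 477. All three match, so for completers the labels W4, W12 and W20 count from the end of the OLTP.

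**2. Put both groups on days since last dose.** Completers: study day − 309.

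| Row | Completers: target | Completers: window | Discontinuers: target | Discontinuers: window |
|---|---|---|---|---|
| FU-W4 | 365 − 309 = 56 | 42 to 83 | 28 | 1 to 56 |
| FU-W12 | 421 − 309 = 112 | not in the text available | 84 | 57 to 112 |
| FU-W20 | 477 − 309 = 168 | 140 to 195 | 140 | 113 to 168 |
| FU > W20 | – | > 195 | – | > 168 |

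Each target differs by 28 days, which is 337 − 309. The missing completers' FU-W12 range may have been lost in text extraction and is not counted as an error.

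**3. Place the end-of-study visit.** 24 × 7 = 168 days. For a discontinuer, day 168 is the last day of FU-W20 and day 169 is FU > W20. For a completer, day 168 is the FU-W20 target, and days 169 to 195 remain FU-W20.

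The ±5-day tolerance is printed for study day 477. Applying it to a discontinuer's visit is an assumption. It gives days 163 to 173, of which 169 to 173 (5 of 11) leave FU-W20. If the protocol's minimum of 24 weeks is kept (168 to 173), only 1 of 6 days is inside. With a window of 140 to 195, none of the 11 days falls outside.

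**4. Disposition.** 23 × 7 = 161 days. If follow-up week 20 in SAP 4.5 is taken from Table 1, a discontinuer last seen 113 to 160 days after last dose counts as having completed follow-up, although the protocol calls that incomplete. One whose final visit is on day 169 or later has no FU-W20 record from that visit, although the protocol calls that complete.

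**5. Overlap of rows.** Double-blind discontinuers stay on the visit schedule to week 24 (Protocol 7.4.2). With a last dose on day 85, the week 16 visit on day 113 is 113 − 85 = 28 days later. It fits both Week 16 (99 to 126) and the discontinuers' FU-W4 (1 to 56). Table 1 gives no precedence.

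**6. Number of patients.** 0.15 × 57 = 8.55, about 9. This is a planning figure and an upper guide, because not every patient who drops out will attend an end-of-study visit.

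**The case against.** The best defence is that little depends on the row. No value is lost, since FU > W20 is a defined row. SAP 5.10 also plots mean concentrations by nominal time and individual concentrations by actual time, and SAP 5.11 lists ADA results by patient and time point. The washout comparison can be recovered from those. This stands, and it is why the point is minor, but the tabulated by-visit means are still split.

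Second, day 168 is inside FU-W20, as are days 161 to 167, which the 23-week rule accepts. This also stands: the claim is exact for visits after day 168, not for every visit actually made.

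Third, SAP 4.5 counts patients who attend the last visit, whereas the protocol counts those with incomplete follow-up. For completers, follow-up week 20 is day 477, or 24 weeks after last dose, so nothing conflicts. For discontinuers the conflict arises only if the count is programmed from Table 1.

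Two stronger readings are not supported. A reader might infer that the mismatched FU-W4 and FU-W12 rows distort safety results. By-visit laboratory and vital-sign tables stop at last dose + 28 days (SAP 5.8.3, 5.8.4), and PCSV and ECG results are incidence tables. Neither PK nor ADA is sampled at the scheduled follow-up contacts before end of study.

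A reader might also infer that closing the TEAE period at last dose + 168 days, when the end-of-study visit has a ±5-day tolerance, is an error. Protocol 10.4.4.1 bases that limit on the expected residual drug effect, and 10.4.4.2 ties PCSV incidence to it, counting unscheduled evaluations too. Stretching it for scheduled visits only would treat values from the same day differently.

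**Conclusion.** The point holds and is minor. Table 1 uses anchors 28 days apart under the same labels, and its discontinuer rows do not fit the protocol's end-of-study timing, contrary to the statement that opens SAP 10.2. A discontinuer's end-of-study visit lands on the limit of FU-W20 or beyond it.

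The consequences are confined to the by-visit row for discontinuers' end-of-study PK and ADA samples and, conditionally, the follow-up completion count. Week-24 efficacy uses Table 2, which has no follow-up rows. Treatment-emergent ADA status depends on any positive post-dose result, not on the row. The number of patients is small and cannot be fixed from the documents.

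The arithmetic assumes completers' last dose is on its scheduled day 309. The share of visits displaced also rests on applying the ±5-day tolerance to discontinuers.

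**What to change.** 1. **SAP Table 1, discontinuer rows.** Set targets to 56, 112 and 168 days after last dose. Use 42 to 83 for FU-W4, the completers' own window for FU-W12, 140 to 195 for FU-W20, and > 195 for FU > W20. Keep the labels. Add an early-termination row for days 1 to 41. This holds an early-termination visit made within 5 days of a next dose missed at the end of its 7-day window (28 + 7 + 5 = 40, an assumption about when stopping is recorded).
2. **Precedence.** State that for double-blind discontinuers the week rows apply first, through the week 24 window, and the follow-up rows after it. One case remains: a patient given only the first dose reaches 168 days on day 169, the week 24 target, and is labelled Week 24. A second dose on day 29 already avoids this (29 + 168 = 197, past day 182). Listing days since last dose beside each sample covers that case.
3. **SAP 4.5 and SAP 7.** Report follow-up completion and insufficient follow-up by the protocol's 23-week rule, or record the change in SAP 1.2.4.
4. **TEAE and PCSV period.** Leave it at last dose + 168 days. Optionally, show end-of-study laboratory and ECG values after that day in a separate descriptive post-treatment table.

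The cost is four edited rows and one new row in Table 1, a precedence sentence, and a sentence for SAP 4.5 and 7. No visit, sample or patient is added, and the change mainly touches second-step outputs.

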10.3. List of AESIs with Data Sources and Definitions of SMQ/CMQ

Table 3: Summary of AESIs and the Methods of Data Collections and Derivations

AESI	Using an e-CRF specific tick box on AE page	Using Standard MedDRA Query (SMQ)/company MedDRA Query (CMQ) or lab data
Anaphylactic reactions	Yes	No
General allergic events	No	SMQ “hypersensitivity” (broad and narrow) excluding the following preferred terms linked to local injection site reactions (“infusion site dermatitis”, “infusion site hypersensitivity”, “infusion site rash”, “infusion site urticaria”, “injection site dermatitis”, “injection site hypersensitivity”, “injection site rash”, “injection site urticaria”, “injection site vasculitis”) plus “idiopathic angioedema”
Infusion reactions	Yes	No

Hepatic Disorders	No	
 • SMQ Drug-related hepatic disorder • Potentially clinically significant value (PCSV) in Appendix 10.4 Hy's law eDISH plot,
Pregnancy	Yes	No
Symptomatic overdose with investigational medicinal product	Yes	No
Neurocognitive events	No	
 • CMQ for neurocognitive events as defined based on Regulatory Agency request for another lipid lowering program (See Table 4 in Appendix 10.3 for the list of terms)
Neurologic events	Yes	No


New onset of diabetes (NOD) for patients without diabetes mellitus at baseline
	
No
	
No medical history of diabetes as specified in Cardiovascular History and Cardiovascular Risk Factors and Medical History CRF pages AND one of the following:
 
Lab criteria: At least 2 values of HbA1c $\geq 6.5\%$ during the TEAE period. NOTE: For patients with only a single measurement available during the TEAE period, a single value $\geq 6.5\%$ will be considered and qualify the patient as NOD by default. For patients with several HbA1c measurements but only with the last one $\geq 6.5\%$, this single value $\geq 6.5\%$ will be considered and qualify the patient as NOD by default.
 
OR
 
Lab criteria: At least 2 values of fasting glucose ≥ 126 mg/dL (7.0 mmol/L). NOTE: For patients with only a single measurement available during the TEAE period, a single value ≥ 126 mg/dL (7.0 mmol/L) will NOT be considered and will NOT qualify the patient as NOD. For patients with several fasting glucose measurements but only with the last one ≥ 126 mg/dL (7.0 mmol/L), this single value ≥ 126 mg/dL (7.0 mmol/L) will NOT be considered and will NOT qualify the patient as NOD.
 
OR
 
HLT Diabetes mellitus (including subtypes)
 
OR
 
Initiation of any new concomitant medication for hyperglycemia during the treatment period

Diabetic complication for patients
	
No
	
For patients with medical history of diabetes as specified in Cardiovascular History and Cardiovascular Risk

with diabetes mellitus at baseline		
Factors and Medical History CRF pages, each of the following criteria will be considered, respectively:
 
 • Diabetes mellitus or diabetic complication TEAEs using HLT Diabetic complications, HLT Diabetes mellitus (incl subtypes), and PTs Blood glucose increases, Glycosylated haemoglobin increased, Hyperglycaemia, Hyperglycaemic unconsciousness, and Hyperglycaemic seizure • Changes in diabetic medication dosage (specifically increases in dosage) or initiation of additional diabetic medication
Pancreatitis	Yes	No
Cataracts	No	HLT Cataract conditions
Immune complex diseases	No	
SMQ (Narrow) Systemic lupus erythematosus
 
SMQ (Narrow) Vasculitis
 
SMQ (Narrow) Guillain-Barre syndrome

Muscle events/CK elevation	No	
 • Lab data analyses (e.g. PCSV) • All preferred terms under system organ class (SOC): Musculoskeletal and connective tissue disorders • Rhabdomyolysis/myopathy (Narrow SMQ)

Table 4: CMQ “Neurocognitive disorders – FDA’s recommendation”

MedDRA level	MedDRA Term Label
PTCD	Amnesia
PTCD	Amnesic disorder
PTCD	Anterograde Amnesia
PTCD	Behavioural and Psychiatric Symptoms of Dementia
PTCD	Change in sustained attention
LLTCD	Cognitive Deterioration
PTCD	Cognitive Disorder
LLTCD	Confusion
LLTCD	Confusion Aggravated
PTCD	Confusional State
PTCD	Delirium
PTCD	Dementia
PTCD	Dementia Alzheimer's type
LLTCD	Dementia Nos
LLTCD	Dementia Nos Aggravated
LLTCD	Dementia of the Alzheimer's type NOS
PTCD	Dementia with Lewy Bodies
PTCD	Disorientation
PTCD	Disturbance in attention
PTCD	Executive dysfunction
PTCD	Frontotemporal Dementia
LLTCD	Global Amnesia
PTCD	Illogical Thinking
PTCD	Impaired reasoning
PTCD	Incoherent
PTCD	Judgement impaired
PTCD	Memory Impairment
PTCD	Mental Impairment
LLTCD	Mental Impairment Nos
LLTCD	Mental State Abnormal Aggravated
PTCD	Mental Status Changes
PTCD	Mini Mental Status Examination Abnormal
PTCD	Presenile Dementia
PTCD	Retrograde Amnesia
PTCD	Senile Dementia
LLTCD	Senile Dementia Nos
LLTCD	Short-term Memory Loss
PTCD	Thinking Abnormal
LLTCD	Thinking Slowed
PTCD	Transient Global Amnesia
PTCD	Vascular Dementia

